9.3.3 Detailed description of variables collected

9.3.3.1 Visits

Information collected relating to each visit (baseline, follow-up, end of observation) includes:

· Date of visit

9.3.3.2 Demography

For demographic/socio-demographic assessment, the following data will be recorded:

- Year of birth
- Age
- Sex
- Race [only where legally permitted]
- Ethnicity [only where legally permitted]

9.3.3.3 Vital signs

Information on vital signs to be documented includes:

- Height
- Weight
- Blood pressure
- Heart rate

9.3.3.4 Disease history

Disease history describes any medical findings that are relevant to the underlying disease and were present before inclusion into the study. Findings and diagnosis meeting the following criteria must be documented:

- Date, tumor stage [tumor, node, metastasis (TNM) and Barcelona Clinic Liver Cancer (BCLC) staging] and Child–Pugh status at initial diagnosis
- Tumor stage (TNM and BCLC), Child–Pugh status and ECOG performance status at the time of initial sorafenib treatment (if applicable)
- Etiology of HCC at the study entry
- Disease extent at the study entry (TNM, BCLC, metastatic lesions, extra hepatic spread, vascular invasion, portal vein thrombosis, tumor morphology)

- Child–Pugh score at the study entry
- ECOG performance status at the study entry
- Social history (smoking, alcohol use)

9.3.3.5 Co-morbidities (medical history, concomitant diseases)

Co-morbidities are any medical findings, whether or not they pertain to the study indication, that were present before the start of therapy with regorafenib, independent of whether or not they are still present. They have to be documented in the Medical History/Concomitant Diseases section. Co-morbidities that resolved more than three years prior to study entry and that are not considered relevant to current treatment do not require documentation.

The conditions of interest, which will be documented in the CRF, include:

- Ascites
- Encephalopathy
- Myocardial infarction
- Deep venous thrombosis
- Pulmonary embolism
- Transient ischemic attack
- · Ischemic stroke
- Cerebral hemorrhage
- Hemorrhage, GI
- Diabetes mellitus type I
- Diabetes mellitus type II
- Hypertension
- · Heart failure
- Phlebitis
- Gastrointestinal ulcer
- Angina pectoris
- Esophageal varices
- Upper GI bleeding

9.3.3.6 Prior and concomitant medication

All medication taken before study start (initiated and stopped before study start) is termed prior medication. Prior medication meeting the criteria listed below are considered to be relevant to the study indication must be documented:

- Treatment for HCC
 - o Previous treatment with systemic therapy (including sorafenib)
 - Drug name
 - Start and stop date
 - Dose(s), including maximum tolerated dose
 - Therapy type and intent of treatment
 - Best response to treatment
 - Date of radiological progression, including type of progression (new lesion, new vascular invasion, progression of target lesion and quantification)
 - Tolerability of systemic treatment, including dose modifications relating to side effects

- Reason for discontinuation
- Previous local therapy
 - Procedure, drug name, dose, embolization agent, and intent
 - Administration date
 - Anatomic location
 - Best response to treatment
- Treatments for indications other than HCC

All medication taken in addition to regorafenib for any indication (either initiated before study start or during the study) is termed concomitant medication and has to be documented.

Information to be collected for medication includes:

- Trade name or INN
- Start date, stop date/ongoing
- Dose
- Unit
- Indication

9.3.3.7 Laboratory parameters

Laboratory parameters to be documented include (if available):

- Date of test
- Platelets
- Hemoglobin
- Erythrocytes
- Hematocrit
- Leukocytes
- International normalized ratio (INR)
- Alanine transaminase (ALT)
- Aspartate transaminase (AST)
- Alkaline phosphatase (ALP)
- Sodium
- Lactate dehydrogenase (LDH)
- Alpha fetoprotein (AFP) and AFP-L3
- C-reactive protein (CRP)
- Gamma-glutamyl-transferase (GGT)
- Creatinine
- Creatinine clearance (CrCl)
- Cholinesterase (ChE)
- Total bilirubin
- Albumin
- Des-Gamma-Carboxy Prothrombin (DCP)/ protein induced by vitamin K absence/antagonist-II (PIVKA-II)

9.3.3.8 Exposure/treatment

Information on regorafenib to be documented include:

- Start and stop date
- Dose modification
- Total daily dose
- Reason for dose modification

9.3.3.9 Assessment of therapy

Information on assessment of therapy to be documented includes:

- Tumor assessment according to criteria used within local guidance
 - Date of assessment
 - Tumor assessment [complete response, partial response, stable disease, or progressive disease (measurement proven or by clinical judgment)]
 - Location of metastases by organ (including lymph nodes)
 - O Vascular invasion (location), portal vein thrombosis, extrahepatic spread
- Child–Pugh classification
- ECOG performance status

9.3.3.10 End of observation

If available, the primary reason for end of observation/study discontinuation should be stated:

- · Regular end of study
- Patient lost to follow-up
- Patient withdrew consent
- Patient died
- Other

9.3.3.11 Adverse events/Adverse events of special interest

(Serious) adverse events need to be collected as described in section 11.2. Information collected includes:

- Diagnosis of AE or symptom (if diagnosis unknown)
- Start and stop date
- Seriousness
- Severity according to National Cancer Institute (NCI) Common Terminology Criteria Adverse Event (CTCAE) v4.03 severity grading
- Relatedness to regorafenib therapy
- Action taken
- Event outcome
- Other specific treatment(s) of AE

9.4 Data sources

The investigator collects historic data (demographic and clinical characteristics) from medical records if available. Likewise, the investigator collects treatment-related data during visits that take place in routine practice. Each patient is identified by a unique central patient identification code, which is only used for study purposes. For the duration of the study and afterwards, only the patient's treating physician or authorized site personnel are able to identify the patient based on the patient identification code.

9.5 Study size

Data collected from 1000 patients with uHCC treated with regorafenib globally should allow for sufficient evaluation of safety monitoring of all treated patients, as well as different subsets of patients, including evaluations between subgroups based on region etc. With this number of patients, it is possible to observe at least one patient with a particular adverse event, if the true incidence rate for the AE is 0.2% (2:1000), with approximately 86% probability. A particular event with a true incidence rate of 0.5% could be observed in at least two patients with 96% probability, and in at least three patients with 87% probability. The following tables show the probabilities of observing one, two, or three patients with the event for different true incidence rates, with a sample size of 1000 patients.

True incidence rate of a particular event (%)	Probability of observing the event in			
	At least one patient	At least two patients	At least three patients	
0.1	0.6323	0.2642	0.0802	
0.2	0.8649	0.5943	0.3233	
0.3	0.9504	0.8013	0.5771	
0.4	0.9818	0.9089	0.7625	
0.5	0.9933	0.9599	0.8760	

The sample size is also supported by the feasibility based on a previous global study in 3000 patients with uHCC who received sorafenib. Based on the information from external experts and market research, we consider 30-35% of patients who are treated with sorafenib would be subsequently treated with regorafenib; therefore, 1000 patients would be feasible for this observational study.

9.6 Data management

A Contract Research Organization (CRO) will be selected and assigned for EDC system development. The CRF will be part of the EDC system which allows documentation of all outcome variables and covariates by all participating sites in a standardized way. Information on the EDC system is available upon request (Table 4, Annex 1). Detailed information on data management, including procedures for data collection, retrieval and preparation are given in the Data Management Plan (DMP), which is available upon request (see Table 4, Annex 1).

For information on quality control, refer to section 9.8.

9.7 Data analysis

9.7.1 Statistical considerations

Statistical analyses will be of explorative and descriptive nature. The study is not aimed to confirm or reject pre-defined hypotheses.

All variables will be analyzed descriptively with appropriate statistical methods: categorical variables by frequency tables (absolute and relative frequencies) and continuous variables by sample statistics (i.e. mean, standard deviation, minimum, median, quartiles, 5th and 95th percentiles, and maximum). Continuous variables will be described by absolute value and as change from baseline per analysis time point, if applicable.

Patients who took at least one dose of regorafenib will be included in the safety analysis set (SAF).

Patients who took at least one dose of regorafenib, did not violate a major inclusion/exclusion criterion, and had at least one follow-up assessment after receiving regorafenib will be included in the full analysis set (FAS).

Safety data will be analyzed on the SAF, effectiveness data on the FAS. Demographic and baseline data will be described for the SAF and the FAS.

All analyses will be performed for the total study population (overall analysis) and separately for each participating country if patient numbers are sufficient and if required for local reasons. Whenever reasonable, data will be stratified by subgroups (e.g. age, gender, baseline characteristics, and prior treatment).

All therapies documented will be coded using the World Health Organization – Drug Dictionary (WHO-DD). Medical history, any diseases and AEs will be coded using the latest Medical Dictionary for Regulatory Activities (MedDRA) version.

All statistical details including violation of inclusion/exclusion criteria and patient validity, derived variables for analysis, handling of missing data, and format and content of tables will be detailed in the Statistical Analysis Plan (SAP). The SAP will be finalized before study database lock. The SAP is available upon request (see Table 4, Annex 1).

It is planned to have an interim analysis/analyses after minimum of 500 patients have been on study for at least 4 months, for the purpose of safety monitoring. The interim analysis will be detailed in the SAP. The final analysis will be performed after end of the study which is the date the analytical dataset is completely available.

9.7.2 Analysis of demography, disease details, prior and concomitant medication and other baseline data

All background data such as patient demographics, diagnosis and prior treatment for HCC, past medical history, concomitant diseases, and concomitant medication will be described by presenting frequency distributions and/or basic summary statistics.

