9.1.2 Secondary endpoint(s)

The secondary endpoints for all patients are:

- Overall survival (OS) is defined as the time (days) from the start of regorafenib treatment to the date of death, due to any reason. Patients alive or lost to follow-up at the time of analysis will be censored at their last date of follow-up.
- Progression-free survival (PFS) is defined as the time (days) from the start of regorafenib treatment to the date of first observed disease progression (radiological or clinical, whichever is earlier) or death due to any cause, if death occurs before progression is documented.
- Time to progression (TTP) is defined as the time (days) from the start of regorafenib treatment to the first documented disease progression.
- Best overall tumor response (ORR) will be defined for all patients using tumor assessment criteria, including modified Response Evaluation Criteria in Solid Tumors (mRECIST).

• Duration of regorafenib treatment, defined by the time interval from the start of regorafenib treatment to the day of permanent discontinuation of regorafenib (including death); mean dose and reasons for regorafenib discontinuation or dose modification will be recorded

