9.2.7 Visits

The start of the study is the date from which information on the first patient can be first recorded in the study dataset (i.e. first informed consent obtained). The end of the study is the date after which the final patient remaining in the study has been in the study for 24 months, or is no longer under observation owing to being lost to follow-up, withdrawal, or death.

A visit is defined as any status assessment or new treatment decision the treating physician takes in the presence of the patient. The time interval between two documented status assessments is assumed to be 6–12 weeks, although this will be at the discretion of the treating physician.

The investigator will document the baseline / initial visit, follow-up visits and the end of observation / final visit for each patient in the CRF. Follow-up visits occur during routine practice; the study protocol does not define exact referral dates for those visits. The end of observation / final visit is to be documented after a patient has been on study for at least 24 months, is lost to follow-up, has withdrawn consent or has died, whichever comes first. If the documentation is stopped prematurely, the reasons for the end of observation must be given. If a patient joins an interventional clinical study during the course of observation, information on survival should be collected up to the end of this study. If a patient remains alive at time of study closure, this will be documented in the final visit.

Table 3: Tabulated overview on variables collected during the study

Variables	Baseline / Initial visit*	Follow-up visit(s)	End of observation / final visit
Visit date	X	X	X
Eligibility assessment	X		
Patient information and consent	X		
Demography	X		
Co-morbidities (medical history, concomitant diseases)	X		
HCC classification	X		
Prior systemic anti-cancer therapy (including sorafenib) (see 9.3.3.6)	X		
Tolerability of prior systemic anti-cancer therapy (including sorafenib) (see 9.3.3.6)	X		
Prior local anti-cancer therapy	X		
Prior medication	X		
Lifestyle records (smoking & alcohol use)	X		
Vital signs	X		
BCLC Staging	X		
Tumor status and metastases (see 9.3.3.9)	X	X	X
Child-Pugh classification	X	X	X

ECOG performance status	X	X	X
Laboratory parameters (see 9.3.3.7)	X	X	X
Concomitant medication	X	X	X
Exposure/treatment with regorafenib (see 9.3.3.8)	X	X	X
Adverse events on regorafenib (see 9.3.3.11)	X	X	X**
Reason for end of observation			X
Death and reason for death			X

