9.7.4 Analysis of secondary outcome(s)

All summaries with respect to the effectiveness data will be descriptive. Effectiveness endpoints include OS, PFS, TTP, and best ORR. Investigator-assessed data, preferably per mRECIST according to local standard, will be used to evaluate the tumor response and radiological progression. Kaplan—Meier (KM) estimates and KM curves will be presented for OS, PFS, and TTP (as appropriate). Radiologically or clinically documented progression of tumor will be considered as disease progression. Subgroup analyses stratified with prognostic/predictive factors collected at baseline as mentioned above may be explored.

OS is defined as the time (days) from the start of regorafenib treatment to the date of death, due to any reason. Patients alive or lost to follow-up at the time of analysis will be censored at their last date of follow-up.

PFS is defined as the time (days) from the start of regorafenib treatment to the date of first observed disease progression (radiological or clinical, whichever is earlier) or death due to any cause, if death occurs before progression is documented.

TTP is defined as the time (days) from the start of regorafenib treatment to the first documented disease progression.

ORR will be defined for all patients using tumor assessment criteria, including mRECIST.

For regorafenib treatment, descriptive statistics will be calculated for the treatment duration, starting dose and average dose. The following frequencies will be calculated for regorafenib treatment: the number of patients with dose modification (e.g. reduction, interruption, re-challenge at protocol dose), number of dose modifications, and frequencies of reasons for dose modifications. These exposure analyses will be performed overall and by prior sorafenib dosing pattern.

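### The FAS requires a follow-up assessment after dosing, so treated patients who die before one drop out of OS, PFS and ORR, which biases these results upward

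*Protocol*

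**What the plan says.** Section 9.7.1 defines two sets. For safety: "Patients who took at least one dose of regorafenib will be included in the safety analysis set (SAF"). The full analysis set adds two conditions to the first dose: no major eligibility violation, and a follow-up assessment ("had at least one follow-up assessment after receiving regorafenib will be included in the full analysis set (FAS"). The sets are then assigned: "Safety data will be analyzed on the SAF, effectiveness data on the FAS". The abstract (section 4) repeats the same rules. Section 9.7.4 lists what this covers: "Effectiveness endpoints include OS, PFS, TTP, and best ORR".

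Section 9.1.2 starts the OS clock at treatment: "Overall survival (OS) is defined as the time (days) from the start of regorafenib treatment to the date of death, due to any reason". PFS has the same start and also counts death: "or death due to any cause, if death occurs before progression is documented". Section 9.1.2 introduces the secondary endpoints as applying to every patient, and section 9.7.4 says the same of ORR.

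Section 9.2.7 describes how follow-up happens: "A visit is defined as any status assessment or new treatment decision the treating physician takes in the presence of the patient". On timing: "The time interval between two documented status assessments is assumed to be 6–12 weeks", at the physician's discretion. Table 3 has one column for follow-up visits and another for the end of observation or final visit. Death and survival status are marked only in the second.

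**The concern.** The follow-up condition can be met only after the OS and PFS clocks have started. Anyone in the set through a follow-up visit must have lived to that visit, which is guaranteed survival (immortal) time. The deaths left out are all early ones, so the error runs in one direction. An excluded early death has a known date, recorded at the end of observation, and both endpoint definitions would count it as an event.

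The study has one arm, so there is no concurrent group in which the same selection would cancel. The protocol also wants results by Child–Pugh group and other subsets. If early mortality differs between subsets, the share excluded differs too, and comparisons between them are distorted. The rule also conflicts with the statements in sections 9.1.2 and 9.7.4 that the endpoints apply to all patients. Section 9.9 mentions selection bias in general and variable visit timing, but not this exclusion. No OS or PFS analysis in all treated patients is stated.

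**Working it through.** The protocol gives no figure on this point. Its one sizing calculation (section 9.5) concerns detecting adverse events. It reproduces, for example 1 − 0.998^1000 = 0.8649, but has no bearing here. The size below is therefore an illustration under stated assumptions.

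**Inputs**
- Median OS 10.6 months with regorafenib, from the phase III trial quoted in section 7. Its placebo median, 7.8 months, serves as a poorer-prognosis value.
- First follow-up at 6 or 12 weeks (section 9.2.7): 6 × 7 / 30.4375 = 1.38 months and 12 × 7 / 30.4375 = 2.76 months.
- Assumed: exponential survival.
- Assumed: a share s of the deaths before the first follow-up is excluded. The documents do not give s, so it is varied.

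**Step 1: deaths before the first follow-up.** λ = ln 2 / 10.6 = 0.0654 per month and F = 1 − exp(−λ·t0).
- 6 weeks: F = 1 − exp(−0.0654 × 1.38) = 8.6%.
- 12 weeks: F = 1 − exp(−0.0654 × 2.76) = 16.5%.

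**Step 2: effect on the OS curve.** With d = s·F excluded, the curve after t0 is S(t)/(1 − d). The median that would be read off is −ln[0.5·(1 − d)]/λ.

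| Share of early deaths excluded | First visit at 6 weeks: d, median | First visit at 12 weeks: d, median |
|---|---|---|
| One quarter | 2.2%, 10.93 months | 4.1%, 11.24 months |
| One half | 4.3%, 11.27 months | 8.3%, 11.92 months |
| All (ceiling) | 8.6%, 11.98 months | 16.5%, 13.36 months |

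Relative to 10.6 months this is +3% to +6%, +6% to +12% and +13% to +26%. Twelve-month survival, truly 45.6%, would read 46.6% to 47.6%, 47.7% to 49.7% and 49.9% to 54.6%. With no exclusion, d = 0 and the assumed 10.6 months is recovered.

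**Step 3: poorer prognosis.** With a true median of 7.8 months, the reading is 8.13 to 8.43 months (a quarter excluded), 8.47 to 9.10 (half) and 9.18 to 10.56 (all).

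**Step 4: simulation check.** With 400,000 patients, a first visit uniform over 6 to 12 weeks and all earlier deaths dropped, 12.7% are excluded. The Kaplan–Meier median is 12.64 months, against 10.57 in the full simulated cohort.

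**Step 5: patients lost with no follow-up.** A patient censored at day 0 is in no later risk set. In the simulation, with 5% lost at day 0, the median is 10.57 months whether they are kept or dropped.

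**Step 6: ORR.** Excluded patients have no response assessment, so removing them multiplies ORR by 1/(1 − d), compared with counting them as non-responders. For the values of d above, the factor runs from 1/(1 − 0.022) = 1.02 to 1/(1 − 0.165) = 1.20. Patients lost before any assessment leave the denominator as well.

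**The case against.** The strongest reply is that the protocol does not define a follow-up assessment. Section 9.7.1 does not say follow-up visit, and Table 3 lists a survival assessment at the final visit, which is documented when a patient has died. If that record counts, early deaths stay in and the OS and PFS bias largely disappears. Section 9.7.1 also leaves details of patient validity to the SAP. This part stands as a real ambiguity. However, the condition itself is already fixed in the protocol, and Table 3 separates follow-up visits from the final visit. The plain reading is therefore exclusion, and nothing in the text says otherwise.

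Second, the ceiling assumes no in-person contact before week 6 or 12. Visit timing is discretionary, and any in-person treatment decision is a visit, so many patients who die early will have had one. That stands, and it is why the range starts at a quarter of the early deaths.

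Third, effectiveness is secondary and descriptive, no comparison with the earlier phase III trial is planned, and section 9.9 warns about historical comparisons. Baseline data are described for both sets, so exclusions will be partly visible. This limits the severity, but a descriptive estimate can still be biased.

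A reader might infer more than the documents support:
- **Early loss to follow-up.** It might seem that dropping patients lost early also raises OS and PFS. Step 5 shows that those lost at day 0 do not move a Kaplan–Meier estimate.
- **Deterioration.** It might seem that patients who deteriorate early are removed. A decision to stop or change treatment with the patient present is itself a visit, so such a patient is lost only if never seen again.
- **TTP.** It might seem to be inflated in the same way. Death is not a TTP event in section 9.1.2, so the argument does not carry over and no TTP bias is shown.

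**Conclusion.** The point holds for OS, PFS and ORR. Followed as written, the FAS rule leaves out treated patients who die before a first follow-up visit. This biases OS and PFS upward, removes early failures from the ORR denominator, and contradicts the statements that the endpoints apply to all patients.

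The direction rests on reading the undefined term as a follow-up visit, which section 9.2.7 and Table 3 favour but do not settle. The size rests on exponential survival, the quoted 10.6-month median, a first visit at 6 to 12 weeks, and an unknown share of early deaths excluded. Under those assumptions the median OS is overstated by about 0.3 to 0.6 months if a quarter are excluded and by 0.7 to 1.3 months if half are. The ceiling is 1.4 to 2.8 months and should not be quoted as the expected bias. The protocol gives no PFS median in HCC, so for PFS only the direction is supported.

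Severity is should-fix. The affected endpoints are secondary and descriptive, and the primary safety analysis uses the SAF.

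**What to change.** In section 9.7.1 and the abstract, do one of the following:
- Drop the follow-up condition for effectiveness, so that OS and PFS are analysed in all patients who took at least one dose, less baseline eligibility violators if wanted.
- Keep the condition but state that a death record counts as a follow-up assessment.

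The first is cleaner because it needs no definition of a follow-up assessment. In either case, keep treated patients without a tumor assessment in the ORR denominator as non-responders, and align sections 9.1.2 and 9.7.4 with the chosen set. The present FAS can remain as a sensitivity set.

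The cost is a few sentences. No new data are needed, because Table 3 already collects death and survival status. The downside is that the reported OS, PFS and ORR will be slightly to moderately less favourable, depending on how many early deaths the present rule would have excluded.
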